# 8. Health Care Professionals Experiences and Expectations

To assess the health care professional's experiences and expectations of hybrid closed loop technology throughout the study.

# **6.3 Study Endpoints**

## **6.3.1 Primary Endpoint:**

The % time sensor glucose level is in target range (3.9–10 mmol/L) during HCL insulin delivery vs standard therapy (MDI and CSII), measured 23-26 weeks post-randomisation.

#### Secondary Endpoints:

#### 1. Glycaemic:

Assess the average difference between standard therapy (MDI and CSII) in the following measures:

#### CGM data:

- a. % CGM Time < 2.8 mmol/L
- b. % CGM Time <3.3 mmol/L
- c. % CGM Time < 3.9 mmol/L
- d. % CGM Time 3.9-7.8 mmol/L
- e. % CGM Time >10.0 mmol/L
- f. % CGM Time >13.9 mmol/L

- g. % CGM Time >16.7 mmol/L
- h. Standard Deviation and Coefficient of Variation of CGM values
- i. Mean CGM glucose
- ii. Average Fasting blood glucose (mmol/L), as measured during the CGM time blocks at baseline, 13 weeks and 26 weeks post randomisation. Defined as fasting capillary blood glucose level on waking (between 5am and 9am), at least 6 hrs after an insulin bolus for carbohydrate.
- iii. Average Glycaemic control as measured by HbA1c collected at baseline, 13 weeks and 26 weeks post randomisation.
- iv. Hospitalisations rate for diabetic ketoacidosis over the 7 month study period.
- v. Events of severe hypoglycaemia over the 7 month study period.

A sub- analysis of HCL vs. MDI and HCL vs. CSII is planned.

NOTE: Ketone measurement is not an outcome measurement in this trial, and all participants will be instructed to measure their ketones as per their routine clinical care.

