Study Design	HCL vs. standard therapy (MDI and CSII), Australian multicentre parallel design study.  Participants will be randomized to use HCL or continue on standard therapy( MDI and CSII)  Minimisation randomisation will be employed, stratifying by time in target glucose range 3.9-10 mmol/L, age, diabetes duration, and centre site.							

	Duration of study – 7 months							
	Enrolment period – 12 months							
Investigational device	MiniMed™ 670G Insulin Pump Hybrid Closed Loop System.							
Hypothesis	1. HCL will increase time in sensor glucose target range (3.9 –							
	10mmol/L) compared to standard therapy.							
	2. HCL will reduce time spent in hypoglycaemic range							
	(<3.9mmol/L) compared to standard therapy.							
	3.HCL will improve glycaemic control as assessed by HbA1c.							
	4. HCL will have a positive impact on quality of life and fear of							
	hypoglycaemia as determined by participant/parent questionnaires							
	5. HCL will be a cost effective intervention for the management of							
Duimour abiactiva	type 1 diabetes compared to standard treatment.  1. The primary objective is to compare the proportion of time							
Primary objective	spent in target glycaemic range (sensor glucose level 3.9 - 10							
	mmol/l) while using HCL or using standard therapy (MDI and							
	mmol/l) while using HCL or using standard therapy (MDI and CSII).							
Secondary objectives	The secondary objectives are to compare the efficacy of the							
٠٠٠٠	MiniMed™ 670G Insulin Pump Hybrid Closed Loop System							
	versus standard therapy (MDI and CSII) by the measurement of							
	the following:							
	1.Glycaemic(24hr, day (0600 – 2400), night (0000 – 0600))							
	CGM data will be collected in three time blocks; baseline (3 weeks							
	CGM), 13 weeks (2 weeks CGM) and 26 weeks (3 weeks CGM)							
	post randomisation. A sub analysis of HCL vs. MDI and HCL vs.							
	CSII is planned.							
	i. CGM data:							
	a. % CGM Time <2.8 mmol/L							
	a. % CGM Time <2.8 mmol/L b. % CGM Time <3.3 mmol/L							
	c. % CGM Time <3.9 mmol/L							
	d. % CGM Time 3.9-7.8 mmol/L							
	e. % CGM Time >10.0 mmol/L							
	f. % CGM Time >13.9 mmol/L							
	g. % CGM Time >16.7 mmol/L							
	h. Standard Deviation and Coefficient of Variation							
	of CGM values							
	i. Mean CGM glucose							
	ii. Average Fasting blood glucose (mmol/L), as measured							

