# 7 Design of the randomized controlled trial

# 7.1 Statement of design and randomisation

This is a prospective, randomized multi-centre study in adult and paediatric subjects from Australia, with type 1 diabetes mellitus aged 12 – 25 years. Participants can be on CSII or MDI treatment regimens to be eligible. After a run-in phase, subjects will be randomly assigned to one of the following two arms:

HCL arm: MiniMedTM 670G for 6 months; OR Conventional arm: MDI or CSII for 6 months.

Randomization will be stratified based on 4 variables: Time spent in target sensor glucose range (3.9 – 10mmol/L) – with participants evenly split above and below 55%(17) time in target range, age, diabetes duration, and centre site. This will be managed by the Clinical Trials Centre in Sydney.

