## 7.4.2 Exclusion Criteria

A subject is excluded from the study if any of the following criteria are met:

- 1. Chronic kidney disease (eGFR <45mL/min/1.73m^2)
- 2. Use of any non-insulin glucose-lowering agent within the past 3 months
- 3. Oral or injected steroid use within the past 3 months
- 4. Pregnancy, or planned pregnancy within study period
- 5. Uncontrolled coeliac disease (not following a gluten free diet), or other untreated malabsorption
- 6. Uncontrolled thyroid disease
- 7. Clinically-significant gastroparesis
- 8. Uncontrolled hypertension (DBP >100 mmHg and/or SBP >160 mmHg)
- 9. History of myocardial infarction, severe uncontrolled heart failure, unstable angina, transient ischaemic attack (TIA), stroke, or thromboembolic disease in the past 3 months.
- 10. Poor visual acuity precluding use of the investigational technology
- 11. Inability or unwillingness to meet protocol requirements (including carbohydrate-counting, CGM use as per allocated study group only).
- 12. Severe or unstable medical or psychological condition which, in the opinion of the would compromise the ability protocol requirements investigator, to meet

Visit Schedule	Pre screening																	
CRF visit number		1	2‡	3	4	5	6*	7*‡	8	9	10	11	12	13	14	15	15a#	16ф
Length of time of visit (hours)		4	2 to 8	2	1.5	1.5	4	0.5 to 8	1	1.5	1.5	4	1.5	1.5	1.5	4	1.5	4
Weeks from Randomisation																		
(+/- 2 week window either side of visit)		-4₹	-3 <del>Y</del>	-3	-2	-1	0	0	4	11	12	13	23	24	25	26	26+1	26
Informed Consent		Х																
Auxological data		Х					Χ					Х						Χ
Diabetes clinical history		Х																
C-peptide	x (local)						Х											
U + Es	х																	
bHCG		Х																
HbA1c	х						Х					Х						х
Blood pressure		Х					Х					Х						х
Total Daily Dose		Х					Х					Х						Х
Carbohydrate Counting			Х															
Insulin pump review			Х						Х			Х						
Pump training								Х										
Logbook data recorded				х	Х	Х		х	Х	Х	Х	Х	Х	Х	Х	Х	Х	Χ
logbook data collected							Х					Х				Х	Х	
CGM				х	Х	Х				Х	Х		Х	Х	Х	+/-x	Х	
Psychology measures		Х					Х					Х				Х		
Modified momentary Sampling								Х	Х	Х	Х	Х	Х	Х	Х	Х	х	
Biomarkers							Х											Х
Semi-structured Interview					_										_			Х

Y Length to randomisation may vary according to education level

HCL outpatient Version Number: 6.0 Version Date: 15/07/2019

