VISIT 2\* (within 4 weeks of Visit 1 run in and education planning)

An individual education program will be planned to occur over the next 2 weeks, and will vary according to the prior knowledge and baseline treatment of that participant.

- i. CSII as baseline treatment
  - a) Carbohydrate Counting: 1 x dietician review (1 -2 hours)
  - b) General pump review:  $1 \times 4$  diabetes educator session (1 4) hours to review pump settings, download capability.
- ii. MDI as baseline treatment
  - a) Carbohydrate Counting: 1-3 x dietician (1 -2 hours) review over a week period (prior to visit 3). This may be extended over a period of 3 weeks if deemed clinically necessary. Participants will be issued with an Aviva Expert (Roche) glucometer and testing strips, which will be programmed with individual carbohydrate ratio, and insulin sensitivity.

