# VISIT 3 (1.5 hrs)

This visit starts the official glycaemic baseline data collection point. This constitutes 21 days of blinded continuous glucose monitoring. The study participant will attend the research facility to have a 4th generation sensor inserted and GST3C minilink attached. Subjects will receive the following instruction:

- i. Expectations of minimum 4x/day glucose testing using CONTOUR® NEXT LINK 2.4 glucometer. Participants will be instructed that an addition to any glucose values recorded on their usual glucometer, they will need 4x additional values (can be taken concurrently) taken on a CONTOUR® NEXT LINK 2.4 glucometer which will be issued to them at this visit.
- ii. Instructed to collect prospective data over the following 21-28 days and record into the diary:
  - 1. Symptomatic hypoglycaemia requiring carbohydrate rescue
  - 2. Time off work / school (including parents)
  - 3. Insulin dosing (MDI participants)
- iii. Instruction on the logbook, with respect to identifying contacts (investigative staff) for trouble shooting and technical issues for the following 21-28 days.

At this visit, all participants will be issued with the following:

- i. Participant logbook
- ii. CONTOUR® NEXT LINK 2.4 glucometer

VISIT 4 and Visit 5 (30 minutes each)

7 days after sensor insertion, participants will return to download the first week of CGM data. The CONTOUR® NEXT LINK 2.4 glucometer will be uploaded. A new sensor will be inserted and a fresh GST3C attached. The logbook will be revised, and participants reminded to keep records accurate and up to date. This is repeated in another 7 days. If there is insufficient CGM data collected by visit 5 (>70% of of each 7 day period having CGM recordings),or due to a technical reason for the CGM data not being available for the minimum amount, participants will be offered additional CGM collection to meet the requirement of the protocol.

HCL outpatient Version Number:6.0 Version Date:15/07/2019

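### DKA hospitalisations and severe hypoglycaemia are counted over a 7-month window that, on the nominal schedule, takes in about 4 weeks before randomisation

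*Protocol*

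**What the plan says.** Two secondary glycaemic endpoints carry an explicit time window. Section 6.3 lists "Hospitalisations rate for diabetic ketoacidosis over the 7 month study period" and "Events of severe hypoglycaemia over the 7 month study period". The same window is given in Section 6.2.2 and in the synopsis, under both objectives and endpoints (the synopsis endpoint list counts hospitalisations for severe hypoglycaemia rather than all episodes). The synopsis also states "Duration of study – 7 months".

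Section 7.1 describes the design differently in time: "After a run-in phase, subjects will be randomly assigned to one of the following two arms", followed by 6 months in each arm, for example "Conventional arm: MDI or CSII for 6 months". The visit table places Visit 1 at week -4, the first baseline sensor at week -3, randomisation (Visit 6) at week 0 and study end (Visit 16) at week 26. Visit 3 opens the baseline sensor block: "This constitutes 21 days of blinded continuous glucose monitoring". The run-in can be longer than nominal. A footnote to the table says "Length to randomisation may vary according to education level", and Visit 2 is placed "within 4 weeks of Visit 1 run in and education planning".

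Section 7.3 plans unadjusted Poisson incidence rates and rate differences for hypoglycaemia hospitalisations, and a tabulation of DKA hospitalisations as number and percentage. It does not say when the at-risk period starts.

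**The concern.** An event before allocation cannot have been caused by the allocated treatment. If the 7 months start at Visit 1, both arms carry the same block of untreated time into the comparison, and the contrast moves towards no difference whether the true effect is benefit or harm.

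The wording stands out against the rest of the protocol. The primary endpoint is timed to weeks 23-26 after randomisation. Fasting glucose and HbA1c, just above these items in Section 6.3, are tied to baseline, 13 weeks and 26 weeks. Hypoglycaemia before allocation already has its own place: a 12-month history of severe events at Visit 1 and a logbook count at Visit 6, collected before randomisation. Only these two items have a window that appears to run across the moment of allocation.

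**Working it through.** **Inputs.** Window for both endpoints: 7 months (synopsis, Sections 6.2.2 and 6.3). Treatment: 6 months per arm after a run-in (Section 7.1). Visit 1 at week -4, randomisation at week 0, study end at week 26 (visit table; Visit 16). Arm entry (Visit 7): at most 2 weeks after Visit 6.

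**Step 1: which interval gives 7 months?** Weeks per month = 365.25 / 12 / 7 = 4.348.

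| Interval | Weeks | Months |
|---|---|---|
| Visit 1 to week 26 | 4 + 26 = 30 | 30 / 4.348 = 6.90 |
| Randomisation to week 26 | 26 | 26 / 4.348 = 5.98 |
| Randomisation, 2-week delay to Visit 7, then 26 weeks | 28 | 28 / 4.348 = 6.44 |

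The stated 7 months is reproduced by run-in plus treatment, and not by treatment alone on the nominal schedule.

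**Step 2: share of the window before allocation.** With r run-in weeks the share is r / (r + 26). At r = 4 it is 4/30 = 13.3%.

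**Step 3: effect on the rate difference.** Let the run-in rate be m in both arms and the post-randomisation rates be a (HCL) and b (control). The observed rates are (r·m + 26·a)/(r + 26) and (r·m + 26·b)/(r + 26). Their difference is 26·(a - b)/(r + 26), because m cancels. The true difference is therefore multiplied by 26/(r + 26), which at r = 4 is 26/30 = 0.867.

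Run-in lengths other than 4 weeks below are assumed, to show the range:

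| Run-in r (weeks) | Share before allocation | Rate difference multiplied by |
|---|---|---|
| 3 | 3/29 = 10.3% | 0.897 |
| 4 (nominal) | 4/30 = 13.3% | 0.867 |
| 6 | 6/32 = 18.8% | 0.813 |
| 8 | 8/34 = 23.5% | 0.765 |

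**Step 4: rate ratio, as illustration only.** If, in addition, the run-in rate equals the control rate (m = b), the observed ratio is (r + 26·RR)/(r + 26). The true ratios are assumed; the documents give none. At r = 4:
- true 0.50 appears as (4 + 13)/30 = 0.57;
- true 2.0 appears as (4 + 52)/30 = 1.87.

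**Step 5: DKA as number and percentage.** Run-in events add the same expected number to each arm. The expected difference in counts is unchanged, but the ratio moves towards 1 and chance variation is added. When counts are small, a few run-in events falling in one arm can change the visible picture.

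**The case against.** **Inclusion of the run-in is inferred.** No sentence says that counting starts at Visit 1. Stacking allowances can produce a 7-month period wholly after randomisation. A 2-week delay to Visit 7, 26 weeks from there and one week for the supplementary sensor visit give 29 weeks; adding the 2-week visit window gives 31 weeks (7.1 months). For participants moving from injections to HCL, counting from Visit 7D instead gives 2 + 4 + 26 = 32 weeks (7.4 months). This stands as a reason for caution. But these are maxima, not the nominal schedule, and Visit 16 is headed as week 26 after randomisation. If this reading was intended, the start of the at-risk period is unclear and the same edit resolves it.

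**The analysis plan may settle it.** Section 7.3 leaves the risk period open, and a protocol commonly leaves such detail to the analysis plan. The window itself, though, is part of the endpoint definition here. An analysis plan counting only from randomisation would depart from the protocol's nominal window.

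**The size is modest.** This stands. No event rate is given, so no practical effect can be shown. With 160 participants and possibly few events, a ratio of 0.57 rather than 0.50 may lie well within sampling error. Section 7.3 also falls back on description when counts are sparse.

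Two stronger readings are tempting and are not supported. A reader might infer that a fixed 7 months from Visit 1 would cut off the last weeks of follow-up after a long run-in. Study end is set at week 26 after randomisation, and the stopping rules in Appendix 15.11 keep randomised participants in the study through that visit. A reader might also infer that safety monitoring is diluted. Serious adverse event reporting and the DSMB rules do not use this window.

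**Conclusion.** The concern holds as a defect of definition with a modest effect. On the nominal schedule the stated window includes about 4 weeks before allocation, 13% of the whole, and Section 7.3 does not correct it. Followed literally, it reduces the incidence rate difference to about 87% of its true value. That figure rests on three things: a 4-week run-in, equal run-in rates in the two arms, and complete follow-up to week 26. The rate ratios above are illustrations that need the further assumption that the run-in rate equals the control rate.

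The shrinkage grows if the run-in is extended. Stacking every maximum interval in the visit text would exaggerate it, since the schedule's own figure is 4 weeks. The 3-week education extension is written for participants on injections, so the shrinkage could also differ between the planned HCL versus MDI and HCL versus CSII sub-analyses. The primary endpoint and the sample size are unaffected.

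**What to change.** In all four places (synopsis objectives, synopsis endpoints, Sections 6.2.2 and 6.3), replace the 7-month window for both endpoints with events from randomisation (Visit 6) to Visit 16 or last contact, whichever is earlier. For rates, use each participant's post-randomisation person-time as the denominator, and say so in Section 7.3. Tabulate events between Visit 1 and Visit 6 separately as baseline data.

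The cost is a wording amendment with the ethics submission or notification that Section 11.6 requires. No visit or measurement is added. Hospitalisations are already reportable as serious adverse events within 24 hours, and severe hypoglycaemia must be tracked by arm for the DSMB rule, so the dates needed should be to hand.

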## 2. *Clinical*:

The difference between HCL insulin delivery vs standard therapy for the following measures

- i) Auxological parameters (height, weight, BMI)
- ii) Insulin delivery: total daily dose , including basal and bolus proportion, carbohydrate ratios and insulin sensitivity

## 3. Psychosocial:

Assess the average difference between standard therapy (MDI and CSII) in the following measures:

- i. **Fear of hypoglycaemia**: Hypoglycaemic Fear Survey-II Worry scale: 17-<25years. Children's Hypoglycaemia Fear survey 12 17 years.
- ii. **Hypoglycaemia Awareness**: Hypoglycaemia Awareness Scale (Gold Score) (all ages)
- iii. **Anxiety**: State-Trait Anxiety Inventory (Child version for 12-15yrs, adult version ≥16-<25yrs)
- iv. **Impact and Satisfaction**: The Diabetes Treatment Satisfaction Questionnaire status and change version (16 <25 years)
- v. **Quality of Life**: 12-<25years: EQ-5D-Y,
- vi. **Diabetes specific quality of life**: PedsQL Child version (12 years) Adolescent version (13 18 years) and young adult version (18 <math><25 years).
- vii. **Diabetes distress:** Problem Areas in Diabetes (Teen version for 12 17 years, standard version  $\geq 17 \langle 25yr \rangle$
- viii. **Participant reported outcome for Automated Delivery system:** INSPIRE Questionnaires: baseline and post-assessment versions Child version (12 year olds), Adolescent version (13-18) and adult version(18-25)
- ix. **Semi structure interview** (all ages post study, PCH only)

# 4. Human-technology interaction:

HCL outpatient Version Number: 6.0

Describe participant technology interaction, adherence patterns and approaches that may improve it.

## 5. Health-economic

The health economic impact of HCL insulin delivery vs standard therapy using data derived from:

- i. QALYs calculated from the EQ-5D
- ii. Hypoglycaemic events and HbA1c
- iii. Participant reporting on work interruption
- Investigator reporting time spent on training, education and support, by the type of health iv. professional resource used
- Diabetes management consumables (glucose strips, ketone strips, batteries, sensors, site v. dressings, lancets, needles, insulin).

## 6. Biomarkers (all ages)

Assess the difference between MiniMedTM 670G Insulin Pump Hybrid Closed Loop System vs standard therapy (MDI and CSII) after 6 months of treatment on the following biomarkers:

- Cell Adhesion Molecules (CAM)S i.
- ii. Soluble vascular cell adhesion molecules sVCAM
- Soluble intercellular adhesion molecules sICAM iii.
- s-e Selectin iv.
- Oxidized Low density lipoprotein v.
- Myeloperoxidase. vi.
- MicroRNA signatures for arterial, renal and retinal complications vii.
- viii. **Telomerase**
- DNA methylation/acetylation ix.
- Glycomark Χ.
- Isoprostanes and proteomics xi.
- Clotting profile xii.

## 7. Performance Parameters

To report the performance of the MiniMedTM 670G Insulin Pump Hybrid Closed Loop System, and components. The following measures will be used:

- i. Proportion of time hybrid closed loop is active
- ii. Unplanned exits from closed loop (n)
- iii. Sensor performance – mean absolute relative difference [MARD], sensor failures (n)
- Insulin delivery line performance reported delivery line failures (n) iv.
  - 8. Health Care Professional Experiences and Expectations To report health care provider's experiences and expectations of hybrid closed loop systems through the study duration

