# Sensitivity analysis

The primary endpoint analysis will be re-run with the PP population as a sensitivity analysis. Secondary endpoints.

Coefficient of variation will be reported for each group: bootstrap methods will be used to estimate variability as appropriate.

Rates of hospitalisations for severe hypoglycaemia and moderate hypoglycaemia as per participant log will be analysed as unadjusted incidence rates based on the Poisson distribution. Incidence rates and incidence rate differences will be presented with their associated 95% confidence intervals calculated as exact Poisson confidence limits(22). In addition, where

HCL outpatient Version Number:6.0 Version Date:15/07/2019 appropriate Poisson or negative binomial regression models will be fitted e.g. moderate hypoglycaemia events from the participant log. If there are a high proportion of zero counts, zero inflated Poisson (ZIP) or zero inflated negative binomial models (ZINB) will be considered. If counts are sparse then rates will be reported descriptively only. Number of hospitalisations due to diabetic ketoacidosis events and other safety outcomes will be tabulated and presented as n and %.

Continuous outcome measures (including psychosocial) collected at baseline and endpoint will be analysed using ANCOVA adjusting for baseline score and site. Measures collected at baseline, 3 months and endpoint (e.g. *HbA1c*, *Fasting capillary blood glucose*, *Mean CGM glucose*, *Hypoglycaemic Fear Survey-II Worry scale*, *Child State-Trait Anxiety Inventory*, *The Diabetes Treatment Satisfaction Questionnaire status and change version*, *Problem Areas in Diabetes, Impaired awareness of hypoglycaemia: GOLD SCORE, INSPIRE questionnaires*) will be analysed using mixed models repeated measures (MMRM) adjusting for baseline score (where appropriate), group, period (baseline, 3 months, 6 months) and site. A random intercept term for 'individual' will also be employed if deemed appropriate. Least square means and least square mean differences and their associated 95% confidence intervals will be presented for each group and between groups. Unstructured covariance matrix will be used unless other covariance structures are more appropriate as determined by the Bayesian information criteria (BIC). Human technology interaction and health care professional experiences and expectations analyses will be reported Exploratory; descriptive analysis.

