A separate economic analysis will be conducted. Using measures (e.g. QALYs calculated from the EQ-5D) collected during the trial.

Performance Parameters will be reported descriptively (n, % for categorical measures and n, mean, median, standard deviation, minimum and maximum for continuous measures)

Subgroup and exploratory analysis

Subgroup analysis will be performed to examine differences in treatment effect based on participant characteristics. Subgroup analysis will be treated as exploratory, with the intent of hypothesis generation. A treatment by subgroup interaction term will be included in the MMRM to assess differential effects by subgroup. Subgroup analyses may include (but not be limited to):

- Age
  - o <12 years
  - $\circ$  >12 years
- BMI category
  - 0 <18
  - $\circ$  18 25
  - o > 25
- Diabetes duration
  - o <6 years
  - o 6 years or longer
- HbA1c at baseline.
  - 0 <8%
  - o 8% or greater

A range of additional exploratory analyses will be conducted. These analyses may include (but not be limited to):

- Differential effects of intervention based on time of day
- Examination of time spent in various glycaemic ranges
- Finer-grained analysis of BGL patterns
- Relationship between CGM usage/adherence and outcomes
- Differences in effect size based on control treatment regimen

Techniques used for subgroup and exploratory analysis will depend upon the distribution of the outcome measure and will include presentation/comparison of unadjusted rates with Poisson confidences limits (or negative binomial models where overdispersion is indicated), measures of central tendency and dispersion, mixed modelling, analysis of covariance, and novel graphical presentation.

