#### ii. THOSE RANDOMIZED TO HCL THERAPY:

MDI to HCL: Participants will require general pump education, and standard insulin pump therapy stabilization prior to HCL initiation.

Visit 7A: DNE initial pump training (8hours) including programming the pump, demonstrating line insertion

Participant will be issued the MinimedTM 670G insulin pump and participant user guide.

Visit 7B: Within the next three days, return to observe line change if required and participant is unconfident. Weekly phone/email contact to support pump transition for the following 2 weeks. Participants will upload their pump weekly. Communication can be more often – as per clinical need, and logged by investigators.

Visit 7C: 2 weeks after pump start: Initiate CGM (2 hours), with training on CGM use, alarm settings, training on CGM insertion and changing sensor. Initial low and high alarms will be set at 4.0mmol/L and 15mmol/L respectively, although these can be changed according to individual preference. Rate alarms, suspend on low and suspend before low functions will not be activated.

At this visit participants will be issued with 4th generation sensors and the GST3C transmitter, as well as CGM user guide and instructions for contact persons to assist any troubleshooting

Visit 7D: 2 – 4 weeks post pump start and stabilization, and a minimum of 3 days CGM, face to face for instruction on how to operate HCL, and HCL initiated (2 hours). There will be opportunity for those unfamiliar with CGM use to practice a sensor change with supervision. Upon HCL initiation, participants will be instructed to avoid excessive exercise for 48hrs while the algorithm adapts.

Further, at this point participants will be issued a new logbook and instructed to prospectively to fill in interruptions from work/school and document any insulin pump technical issues (insulin infusion site failures, sensor changes, unplanned exit from HCL). Participants will subsequently have weekly communication via phone call or email for support for the following 4 weeks, and upload their pump weekly. Investigators will log all time spent training and communication with participant. Communication can be more often – as per clinical need, and logged.

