# Stopping Rules:

The DSMB will be responsible for the points above on a regular basis, and will report to the ethics committees and investigators if stopping the trial is required. Pre-defined stopping rules include:

In general, once a subject is randomized, he/she will remain in the study through the 26-week visit unless the investigator believes it is not safe for the subject to continue. However, the criteria below will be used to determine whether use of the HCL should be discontinued for a subject.

Rules for stopping bionic pancreas use for an individual subject are as follows:

- 1. Severe hypoglycemia
- 2. The participant withdraws consent for CHL use
- 3. Participant pregnancy

4. Noncompliance with the protocol or development of a new medical condition or need for chronic use of a medication which in the judgment of the investigator increases risk for the subject

If HCL use is stopped according to the above criteria, but the subject is willing, they will remain in the trial and will continue to make all of the scheduled visits and participate in all monitoring. The primary analysis will be intention to treat. Since subjects in the usual care arm are following their normal diabetes care regimen, there will be no change in their participation in the trial if they experience one of the events that would trigger stopping.

Study participation is voluntary, and subjects may withdraw at any time.

Criteria for Suspending/Stopping Overall Study

The DSMB will have the responsibility of determining if the overall study should be stopped. In case of a recurring system malfunction or participant safety issue observed with multiple subjects, the overall study will be suspended while the problem is diagnosed. The study may resume if the underlying problem can be corrected by a protocol or system modification that will not invalidate the results obtained prior to suspension.

An instance of severe hypoglycaemia in the HCL group will result in temporarily stopping additional enrolment of subjects until DSMB review of the data to determine whether the event was triggered by the system or not and whether it is safe to proceed.

The currently-enrolled subjects will continue use of the system during this time unless the DSMB determines it is unsafe for them to do so.

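### Unplanned closed-loop exits are summarised as raw counts that are not tied to each participant's closed-loop time, so low use can look like good performance

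*Protocol*

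**What the plan says.** The performance measures appear in the synopsis, in section 6.2.2 (item 7) and in section 6.3 (item 7). The section 6.3 list has four entries:

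- "Proportion of time hybrid closed loop is active"
- "Unplanned exits from closed loop (n"
- sensor performance, given as "mean absolute relative difference [MARD], sensor failures (n"
- line performance, given as "reported delivery line failures (n"

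The exits, sensor failures and line failures are therefore each named as a number of events. Section 7.3 gives the summary: "Performance Parameters will be reported descriptively (n, % for categorical measures and n, mean, median, standard deviation, minimum and maximum for continuous measures". Neither section divides the three counts by closed-loop time, sensor wear, pump wear or items used.

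For hypoglycaemia events the same section does name a rate: these "will be analysed as unadjusted incidence rates based on the Poisson distribution", with exact limits.

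Three other parts of the protocol bear on loop time:

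- The Visit 7 schedule starts the loop for former MDI users "2 – 4 weeks post pump start and stabilization, and a minimum of 3 days CGM". For former CSII users it starts after 3 to 7 days of CGM.
- The stopping rules in appendix 15.11 let HCL be discontinued for an individual. If willing, "they will remain in the trial and will continue to make all of the scheduled visits".
- The weekly app in appendix 15.9 asks HCL users whether they have stopped using the loop, and why.

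**The concern.** A count of events describes reliability only if everyone had about the same opportunity to have the event. For unplanned exits the opportunity is time with the loop active, and the protocol itself makes that time unequal through the start date, through individual discontinuation and through ordinary variation in use. Someone who gives up the loop after a few weeks contributes few exits, and a mean or median over such people falls for a reason unrelated to how well the system holds closed loop.

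At stake is the descriptive answer to the performance objective, chiefly for exits.

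Sensor and line failures have a related but separate problem. Their counts rise with the number of sensors or infusion sets used and with wear time, so they too need a denominator, but closed-loop time is not the right one.

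**Working it through.** The protocol states no figure for exits, so there is no number to reproduce. The check has two parts: what the schedule implies for possible loop time, and how a count behaves when active time varies.

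**1. Possible closed-loop days by week 26**

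Inputs from section 7.4, Visit schedule:

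- Final CGM visits are timed from Visit 7a, ending at week 26: 26 × 7 = 182 days.
- Former MDI users: CGM starts at Visit 7C, 2 weeks after pump start, and at least 3 days of CGM must precede Visit 7D. The earliest loop start is day 14 + 3 = 17; the latest is 4 weeks = day 28.
- Former CSII users: loop start on day 3 to day 7.

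Possible loop days = 182 − start day:

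| Previous regimen | Earliest start | Latest start |
|---|---|---|
| MDI | 182 − 17 = 165 | 182 − 28 = 154 |
| CSII | 182 − 3 = 179 | 182 − 7 = 175 |

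Smallest gap: 165 / 175 = 0.94, about 6% less. Largest gap: 154 / 179 = 0.86, about 14% less.

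**2. How the count depends on use**

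Expected count = r × T × s, where r is exits per active day, T is days followed and s is the share of time the loop is active. The protocol gives neither r nor s, so both are assumed. T is set to 182 for simplicity.

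| r (assumed) | s = 30% | s = 50% | s = 70% | s = 90% |
|---|---|---|---|---|
| 0.1 | 5.5 | 9.1 | 12.7 | 16.4 |
| 0.5 | 27.3 | 45.5 | 63.7 | 81.9 |
| 1.0 | 54.6 | 91.0 | 127.4 | 163.8 |

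Within each row reliability is the same, yet the count at 90% is 0.9 / 0.3 = 3 times that at 30%. This ratio does not depend on r. Dividing each count by active days, T × s, returns r in every cell.

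Early stopping acts the same way. At r = 0.5 and 90% use, a participant who stops after 4 weeks has 0.5 × 28 × 0.9 = 12.6 exits, against 81.9 for one who continues.

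The order can even reverse. A participant with 1.0 exit per active day and 30% use has 1.0 × 182 × 0.3 = 54.6 exits. One with half that rate and 80% use has 0.5 × 182 × 0.8 = 72.8. The less reliable experience has the smaller count.

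**3. Whether the same argument covers the other two counts**

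A line can fail whenever a pump is worn: CSII controls are also asked to log infusion site failures, and HCL participants wear the 670G before the loop starts. A sensor can fail whenever it is worn, and CGM also precedes loop start. Leaving the loop while still wearing pump and sensor need not lower either count. The exposures are pump-days or sets, and sensor-days or sensors.

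**The case against.** **Rates could be left to the SAP.** The SAP is not shown, the section 7.3 wording is a generic descriptive template, and nothing forbids a rate. It is true that an SAP could add rates without conflicting with the protocol. But the protocol is not silent: it names the metric as a count and names its summary, and in the same section it specifies incidence rates where it wants them.

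**Exposure is reported.** The proportion of time active heads the same list, so a reader would see low use beside low counts. This stands in part, and it would be wrong to infer that the protocol ignores exposure. If everyone were followed for the same time, the mean count and mean proportion would together give the pooled rate. Follow-up will not be equal, since 20% drop-out is predicted and loop start varies. Medians, SDs and ranges of the two quantities cannot be combined into rates, and nothing links count and use within a participant.

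**Closed-loop use does not drive all three counts.** This stands. A reader might infer that using the loop less makes sensor and line failures look better as well; the schedule and logbook instructions do not support that.

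**Nothing is tested.** This stands too. The stated aim is to report performance. No hypothesis, between-arm test or comparison of former MDI with former CSII users rests on these measures; the planned MDI and CSII sub-analyses are glycaemic and compare HCL with each control regimen. A reader might infer that the performance objective will be answered in the wrong direction, but no directional question is posed. The reversal above shows only what can happen under assumed values.

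**Conclusion.** The point holds for unplanned exits, and it is minor. The stated metric mixes reliability with amount of use. The only part of the size that comes from the protocol is the start delay: 6-14% less possible loop time for former MDI users, assuming the 26 weeks run from Visit 7a and the stated start windows are kept. The larger spread, 3-fold between 30% and 90% use, rests on assumed use shares, although its proportionality holds for any constant exit rate.

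Sensor and line failure counts also lack a denominator, but theirs are items used or wear time, not closed-loop time.

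These are descriptive secondary measures. The primary endpoint, the sample size and all planned tests are untouched.

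**What to change.** In sections 6.3 and 7.3, keep the three counts and report beside them:

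- unplanned exits per 100 days of active closed loop;
- sensor failures per 100 sensors used, or per 100 sensor-days;
- line failures per 100 pump-days, or per 100 sets used.

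Each denominator should cover the same period as its count. HCL participants receive the logbook for technical issues only when the loop is started (Visit 7D or 7B), so logbook-based line failures should be divided by pump-days from that date, not from pump start.

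Pump uploads and the consumable records (sensors and pump sites) listed among the synopsis's continuous assessments should supply the denominators. The cost is a few words of protocol or SAP text and a few lines of programming, with no new data collection.
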